5.2.2. Definitions and Conventions

The following definitions and data handling conventions will be used in the analysis.

Table JZDA.5.1. Definitions and Data Handling Conventions

Term	Definition or Rule
Relative Study Day	If assessment is on or after date of first dose then $(\text{date of assessment}) - (\text{date of first study drug dose}) + 1$
	If assessment precedes first dose of drug then $(\text{date of assessment}) - (\text{date of first study drug dose})$
	There is no study day 0. Study day 1 is the date of first dose and study day -1 is the day before the first dose.
Cycle Day	If assessment is on or after date of first dose in cycle then $(\text{date of assessment}) - (\text{date of first study drug dose in cycle}) + 1$
	There is no cycle day 0. Cycle day 1 is the date of first dose in that cycle.
Baseline	For change from baseline analyses, baseline value is defined as the last reported measure on or before the first dose date (prior to the dose administration), unless otherwise specified.
Age (years)	Age is based on date of birth and Informed consent date. If only a year and month are provided in the date of birth, set day to 15. If only a year is provided, set day to 1 and month to 7 (July).
Duration	Duration (days): $(\text{End Date} - \text{Start Date} + 1)$ Duration (weeks): $(\text{End Date} - \text{Start Date} + 1)/7$ Duration (months): $(\text{End Date} - \text{Start Date} + 1)/30.4375$ (Days in months = $(1/12) * \text{average number of days in a year}$) Duration (years): $(\text{End Date} - \text{Start Date} + 1)/365.25$ (Average days in a year = 365.25, reflecting the Julian Year of 3 years with 365 days each and 1 leap year of 366 days)
Time-to-Event	The event or censoring time (days) is calculated as: $\text{Date of event/censoring} - \text{Date of first dose of study drug} + 1$

5.3. Adjustments for Covariates

Given the small sample size for each tumor type and treatment, no formal analysis investigating the impact of covariates is planned. If data warrant, exploratory analyses may incorporate patient disease characteristics in evaluation of efficacy parameters.

5.4. Handling of Dropouts or Missing Data

Missing data, except for dates, will not be imputed. They will be kept as missing in the data analyses, except for dates when used in calculations of relative study day, for which sponsor reporting standards will be utilized for imputation rules, defined as: Missing start days will be replaced with 1 and missing day/month with 01 JAN. Missing end days will be replaced with the

last day of the month, and missing day/month with 31 DEC. The imputation rule may be updated at the time of study reporting if necessary to maintain accordance with most recent sponsor standards. Partial dates should be reported in all listings and not the imputed date.

For time-to-event endpoints, the method for handling missing data will be censoring. Additional sensitivity analyses may be conducted applying different censoring rules if data warrant and will follow sponsor defined standards.

5.5. Multicenter Studies

Given the small number of patients for each tumor type and treatment, patients across all sites will be grouped together for analysis purposes.

5.6. Multiple Comparisons/Multiplicity

No formal hypothesis testing is planned for this study; thus, there will be no adjustments for multiplicity.

5.7. Patient Disposition

Patient disposition will be summarized and listed for all patients entered into the study. It will include a summary of the number and percentage of patients entered into the study, enrolled in the study, and treated as well as number and percentage of patients completing the study, or discontinuing (overall and by reason for discontinuation of study drug). All patient discontinuation data collected on the case report form (CRF) will be listed.

Important protocol deviations that potentially compromise the data integrity and patients' safety will be summarized for safety population. These deviations will include those that can be identified programmatically and those that can only be identified by the clinical research associate during monitoring. Important protocol deviations are described in another document within the study Trial Master File.

5.8. Patient Characteristics

Patient characteristics will be summarized and listed for safety population. Details of the patient characteristics are described in the following sections. Other patient characteristics will be summarized as deemed appropriate.

5.8.1. Demographics

Patient demographics will include sex, race, ethnicity, country, age, age group (<65 years; ≥65 years, <70 years; ≥70 years), height, weight, body mass index (BMI).

5.8.2. Baseline Disease Characteristics

Baseline disease characteristics will include Eastern Cooperative Oncology Group (ECOG) performance status (PS), initial pathological diagnosis, basis for initial diagnosis, disease stage, histopathological grade, tobacco usage (never, current, former), and alcohol use.

5.8.3. Prior Therapies

Prior radiotherapy, surgery, and systemic therapy will be summarized. Prior radiotherapy will be categorized by reason (neoadjuvant, adjuvant, neoadjuvant plus adjuvant, advanced/metastatic) for the regimen and prior surgery will be categorized by intent (curative, palliative). Prior systemic therapies will be categorized by setting (neoadjuvant, adjuvant, locally advanced, metastatic). Frequency of each specific therapy will be tabulated within each type of regimen and reason for regimen.

The patients who received any prior anti-PD-1 and/or anti-PD-L1 therapies will be listed.

5.8.4. Historical Illnesses

Historical illnesses are events in the past that ended before the date informed consent is signed. Historical illnesses (coded according to the Medical Dictionary for Regulatory Activities [MedDRA] dictionary) will be listed for all enrolled patients.

5.9. Treatment Compliance

LY3415244 will be intravenously administered only at the investigational sites. As a result, patient compliance will be ensured. If there are any cases deemed as not compliance, they will be reported as protocol deviations.

5.10. Concomitant Therapy

Concomitant medications will be summarized and listed for the safety population.

For corticosteroids and/or immunosuppressives, the indication, administration route, individual dose, duration, and dose adjustment reason of the use will be summarized and listed.

5.11. Postdiscontinuation Therapy

The numbers and percentages of patients reporting postdiscontinuation therapies will be provided overall, by type of therapy (surgery, radiotherapy, or systemic therapy), and by drug name.

5.12. Safety Analyses

All patients who receive any quantity of LY3415244 will be evaluated for safety and toxicity. Details of the analyses are described in the following subsections.

5.12.1. Extent of Exposure

A summary of exposure will be provided for study drug, including cycle received, cumulative dose and duration of therapy. Duration of therapy is defined as Discontinuation date - Date of first dose + 1.

A summary of dose intensity will be provided for study drug. Dose intensity expressed in mg/week will be calculated as the actual cumulative amount of drug taken divided by the duration of exposure in weeks. Duration of exposure in weeks is defined as (Date of last dose – Date of first dose + 14)/7.

Relative dose intensity will be calculated as:

$$100\% \times (\text{actual cumulative dose taken [mg]} / \text{planned cumulative dose [mg]})$$

Note that planned dose is the same as actual dose if there is no dose modification or cycle delay.

A summary of dose adjustments will be provided for study drug, including dose omissions, dose reductions, dose increase, dose delays, treatment interrupted and the corresponding reasons for dose adjustments for each cohort.

5.12.2. Dose-Limiting Toxicity and DLT-Equivalent Toxicities

The definition of the DLTs and the DLT-equivalent toxicities (DETs) is specified in Protocol J1C-MC-JZDA (JZDA), Section of Dose-Limiting Toxicity Determination.

Dose limiting toxicities will be summarized and listed for DLT-evaluable population.

Dose limiting toxicities-equivalent toxicities (DETs) will also be listed and summarized for safety population.

5.12.3. Adverse Events

A listing of all adverse events (AEs) by patient will be presented. This listing will include patient number, AE (reported term and Preferred Term [PT]), event start and end dates, Common Terminology Criteria for Adverse Events (CTCAE) grade, relationship to study drug/procedure, seriousness, and outcome. A listing of serious adverse events (SAEs) will be produced using the similar format.

An overall summary will be provided for AEs. The summary will provide counts for all AEs, and AEs related to study treatment. Specifically, the number and percent of evaluable patients will be summarized by treatment for each category below:

- patients with at least one treatment-emergent AE (TEAE)
- patients with at least one Grade 3 or higher TEAE
- patients with at least one SAE
- patients who discontinued due to AE
- patients who discontinued due to SAE
- patients who died due to AE on study treatment
- patients who died due to AE within 30 days of discontinuation from study treatment

The following summaries will also be produced:

- summary of all preexisting conditions
- summary of TEAEs by PT (any grade and Grade ≥ 3)
- summary of TEAEs by System Organ Class (SOC) and PT (any grade and Grade ≥ 3)
- summary of TEAEs by SOC and PT and maximum grade (1-5)

- summary of treatment-emergent SAEs by SOC and PT (any grade and Grade ≥ 3)
- summary of AEs as reason for study treatment discontinuation by SOC and PT
- summary of TEAEs leading to dose omissions, reductions, hospitalizations

In addition, immune-related adverse events (irAEs) may be summarized. A list of what is considered an irAE will be defined in a separate document.

5.12.4. Deaths

All deaths recorded in this study will be included as part of the complete AE listing, where appropriate, and listed separately. A summary of deaths may be presented for all patients on therapy if there are a sufficient number of events for this to be deemed useful.

5.12.5. Clinical Laboratory Evaluation

All laboratory results will be reviewed using Spotfire to assess changes over time and differences between cohort/dose levels. Key findings will be summarized in tables and/or illustrated graphically using line plots over time or box plots, for example.

Any abnormal results of clinical laboratory tests will be listed for all patients on therapy and where appropriate the calculated CTCAE grades using CTCAE v4.0 (or higher) will be given. Calculated CTCAE grades will also be summarized by cohort/dose level for laboratory parameters where CTCAE grades are available. A shift table of baseline grade by maximum postbaseline grade will be produced.

5.12.6. Vital Signs and Other Physical Findings

All vital sign results will be reviewed using Spotfire to assess changes over time and differences between cohorts/dose levels. Key findings will be summarized in tables and/or illustrated graphically using line plots over time or box plots for example.

Any significant physical examination findings and results will be listed.

5.12.7. Electrocardiograms

Any abnormal electrocardiogram (ECG) data based on local testing will be listed and summarized for safety population. Further exploratory analyses may be conducted as warranted.

5.13. Efficacy Analyses

All efficacy analyses will be performed on the safety population. This study is not designed to perform hypothesis testing on efficacy; however, all efficacy data will be listed and summarized.

Response Evaluation Criteria in Solid Tumors (RECIST) 1.1 (Eisenhauer et al. 2009) will be applied as the primary criteria for assessment of tumor response. Local tumor imaging (investigator assessment with site radiological reading) will be used. Modified RECIST (Byrne and Nowak 2004) will be applied for patients with pleural mesothelioma. For the patients with both pleural mesothelioma and solid tumors, Modified RECIST will be applied to pleural mesothelioma and RECIST 1.1 will be applied to the solid tumors.

Two sets of analyses will be provided, with 1 set based on RECIST 1.1 and the other set based on RECIST 1.1 with confirmatory scan for disease progression. The notation “ir” will be used to denote the analyses based on RECIST 1.1 with confirmatory scan for disease progression, it does not indicate that any of the assessments based on irRECIST, irRC, or iRECIST will be used in the study or analyses.

5.13.1. Tumor Measurement

For the patients with solid tumors only (assessed by RECIST 1.1), the tumor size is the sum of the uni-dimensional measurements for each lesion.

For the patients with pleural mesothelioma only (assessed by modified RECIST), the tumor size is the sum of the 6 pleural unidimensional measurements (2 positions, each with 3 levels).

For the patients with both pleural mesothelioma (assessed by modified RECIST) and solid tumors (assessed by RECIST 1.1), the tumor size is the sum of 2 parts, the sum of the 6 pleural unidimensional measurements (2 positions, each with 3 levels) and the sum of the uni-dimensional measurements for each solid lesion.

Individual changes in the tumor size over time will be presented graphically by waterfall and spider plots within a tumor type.

5.13.2. Objective Response Rate and Disease Control Rate

Objective response rate (ORR) and disease control rate (DCR) are summary measures of best overall response (BOR) as defined by RECIST 1.1. Best overall response is derived from time point responses. All time point responses observed while on study treatment and during the short-term follow-up period will be included in the derivation. Patients' responses after objective progression or start of new anticancer therapy are excluded from the determination of best response. Best overall response of complete response (CR) and partial response (PR) should be confirmed by repeated assessment at least 4 weeks following the initial observation. Each patient's BOR will be categorized as CR, PR, stable disease (SD), partial disease (PD), or not evaluable (NE). If appropriate, the best overall tumor response may be calculated by Lilly using all available lesion measurement data to confirm the investigator assessments.

Objective response rate (ORR) will be estimated by dividing the total number of confirmed responders (CR+PR) by the number of enrolled patients who have received any quantity of study treatment.

Disease control rate (DCR) is defined as the number of patients with stable disease, confirmed partial response or confirmed complete response (CR+PR+SD) divided by the number of enrolled patients who have received any quantity of study treatment.

The estimates of ORR and DCR along with exact 95% confidence interval (CI) will be reported.

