Sample collection											See Appendix 4 for pharmacodynamics, pharmacokinetics, immunogenicity, pharmacogenetics, tumor tissue, and other biomarkers.
Administer LY3415244			X	X	X	X	X	X	X	X	LY3415244 will be administered as an IV infusion over approximately 60 minutes, depending on dose level (doses ≤ 70 mg may require bolus IV injection administration over 5 to 10 minutes). In Cycles 1 to 3, the LY3415244 infusion will be followed by a 4-hour observation period.

Baseline and On-Study Treatment Schedule of Activities

Abbreviations: AE = adverse event; C1D1 = Cycle 1 Day 1; CTCAE = Common Terminology Criteria for Adverse Events; ECG = electrocardiogram; ECHO = echocardiogram; ECOG PS = Eastern Cooperative Oncology Group performance status; ESR = erythrocyte sedimentation rate; HCC = hepatocellular carcinoma; HIV = human immunodeficiency virus; ICF = informed consent form; IV = intravenous; MUGA = multiple-gated acquisition; Q = every; RECIST 1.1 = Response Criteria in Solid Tumors Version 1.1; W = weeks.

Table JZDA.2.2. Poststudy Treatment Follow-Up Schedule of Activities

Procedure	Follow-Up Visit				Instructions	
	Short-Term ^a			Long-Term (Q90D) ^b		
	30-Day Visit	60-Day 801	90-Day 802			
Pregnancy test	X		X		Perform pregnancy test for women of childbearing potential	
ECG					See Appendix 4 for ECG collection instructions	
Physical examination	X				Including weight and vital signs (temperature, blood pressure, pulse rate, and respiration rate)	
Concomitant medication	X					
AE collection	X	X	X	X	CTCAE Version 4.0. During the 30-, 60-, and 90-day follow-up visits, collect all AEs/SAEs. Thereafter, collect only SAEs related to study treatment or protocol procedures	
ECOG performance status	X					
Tumor imaging/assessment	X				For patients who discontinue study treatment without objectively measured PD, continue to perform tumor assessment and imaging every 6 to 12 weeks according to the standard of care	
Collection of survival information	X	X	X	X	In-person office visits are not required; the site may confirm survival by contacting the patient directly via telephone or other means of communication (for example, email)	
Collection of poststudy-treatment anticancer therapy information	X	X	X	X	Discontinuation from study treatment must occur prior to introduction of the new agent	
Laboratory tests	X				Perform hematology, coagulation, clinical chemistries, and thyroid function tests	

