Sample collection					See Appendix 4 for pharmacodynamics, pharmacokinetics, immunogenicity, and other biomarkers	

Poststudy Treatment Follow-Up Schedule of Activities

Abbreviations: AE = adverse event; CTCAE = Common Terminology Criteria for Adverse Events; D = day; ECG = electrocardiogram; ECOG = Eastern Cooperative Oncology Group; PD = progressive disease; SAE = serious adverse event; Q = every; W = week.

- a Short-term follow-up begins when the patient and investigator agree that the patient will discontinue study treatment and ends on the day of the 90-day follow-up visit. No follow-up procedures will be performed for a patient who withdraws informed consent unless he or she has explicitly provided permission and consent.
- b Long-term follow-up begins the day after the patient completes the 90-day follow-up visit and ends with the patient's death, upon loss to follow-up, or upon overall study completion, whichever is earlier. No follow-up procedures will be performed for a patient who withdraws informed consent unless he or she has explicitly provided permission and consent.

Table JZDA.2.3. Continued Access Schedule of Activities

Visit	Continued Access Treatment		Continued Access Follow-Up Visits ^a			Instructions: 
 • No follow-up procedures will be performed for a patient who withdraws informed consent unless he or she has explicitly provided permission and consent • Efficacy assessments will be done at the investigator's discretion based on the standard of care.
			30-Day	60-Day	90-Day	
	501-5XX	901	902	903		
Procedure	D1	D15				
AE collection	X	X	X	X	X	As part of AE collection, monitor vital signs and perform standard laboratory tests (hematology, chemistry, urinalysis, and pregnancy testing) at the same frequency as during the study treatment period (see Table JZDA.2.1). All laboratory tests during the continued access period will be performed in the local laboratories only.

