9.1. Efficacy Assessments

Tumor assessments will be performed for each patient at the times shown in the Schedule of Activities (Section 2). A secondary objective of the study is to document efficacy.

RECIST 1.1 (Eisenhauer et al. 2009) will be applied as the primary criteria for assessment of tumor response and disease progression. Local tumor imaging (investigator assessment with site radiological reading) will be used. Modified RECIST will be applied for patients with pleural mesothelioma whereby tumor thickness (perpendicular to chest wall or mediastinum) would be measured at 2 positions on 3 separate levels on transverse cuts of CT scan (Byrne 2004).

Computed tomography (CT) is the preferred imaging method for the majority of patients. Magnetic resonance imaging should only be used when CT is contraindicated or for imaging in the brain. The same imaging technique should be used for a patient throughout the trial. Imaging should include the chest, abdomen, and pelvis. Intravenous and oral contrast is required unless medically contraindicated.

At Study Baseline:

- Must be performed within 28 days prior to the first dose of study drug.
- Scans performed as part of routine clinical management are acceptable for use as initial tumor imaging if they are of diagnostic quality and performed within protocol-required time frame as described above.

During Study Treatment:

- Performed every 8 weeks (± 7 days), by the investigator, with confirmatory assessment obtained at the next routine scheduled imaging time point.
- Per RECIST v1.1, PR or CR should be confirmed by a repeat tumor imaging assessment, preferably at the next scheduled imaging visit, and not less than 4 weeks from the date the response was first documented. Thus, for Study JZDA, tumor imaging for confirmation of response may be performed at the earliest 4 weeks after the first indication of response, or at the next scheduled scan, whichever is clinically indicated.
- Continue to perform imaging until whichever of the following occurs **first**:
 - disease progression confirmed by the second radiographic examination

- the start of new anticancer treatment
- withdrawal of consent
- death
- study completion

If radiologic imaging verifies an initial assessment of PD, apply RECIST 1.1 with confirmatory scan for disease progression (Section 9.1.1).

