During the Poststudy Treatment Period: Tumor assessments may continue for patients who are withdrawn from the study treatment for reasons other than disease progression every 6 to 12 weeks depending on standard of care.

See Section 10.3.2 for definitions of the efficacy endpoints.

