9.1.1. RECIST 1.1 with Confirmatory Scan for Disease Progression

9.1.1.1. Rationale for RECIST 1.1 with Confirmatory Scan for Disease Progression

Response to immunotherapy may differ from responses typically observed with cytotoxic chemotherapy, including the following (Wolchok et al. 2009; Nishino et al. 2013):

- Response to immunotherapy may be delayed.
- Response to immunotherapy may occur after PD by conventional criteria.
- The appearance of new lesions may not represent PD with immunotherapy.
- Stable disease while on immunotherapy may be durable and represent clinical benefit.

Therefore, to adequately characterize additional patterns of response and progression specific to patients treated with immunotherapy, which cannot be captured by conventional criteria such as RECIST 1.1, alternative measures of tumor assessment have been developed: (i) RECIST 1.1 with confirmatory scan for disease progression and (ii) immune-related response criteria (irRC, Wolchok et al. 2009). For both measures (i) and (ii), clinically stable patients may continue treatment until disease progression (per standard RECIST 1.1) is confirmed. As the irRC are still being developed and validated for various tumor types, Study JZDA will use RECIST 1.1 with confirmatory scan for disease progression, which may discourage the early discontinuation of study treatment and provide a more complete evaluation of its efficacy than would be seen with conventional response criteria.

Table JZDA.9.1. Summary of Response Assessment by RECIST, RECIST with Confirmatory Scan for PD, and irRC

Definition	Used in Study JZDA		Not Used in Study JZDA
	RECIST v1.1	RECIST 1.1 with Confirmatory Scan for PD	irRC (Wolchock et al. 2009), irRECIST (Nishino et al. 2013) iRECIST (Seymour et al. 2017)
New lesion	The presence of new lesion defines progression	The presence of new lesion defines progression	The presence of new lesion does not define progression. The measurements of the new lesion(s) are included in the sum of the measurements.
Confirmation of PD	Not required	PD, in the absence of clinically significant deterioration, requires confirmation with repeat imaging after 4-6 weeks. After initial PD following RECIST v1.1, shift to “RECIST 1.1 with confirmatory scan for PD”.	Required

Abbreviations: irRC = immune-related response criteria; irRECIST = immune-related Response Evaluation Criteria in Solid Tumors PD = progressive disease; RECIST = Response Evaluation Criteria in Solid Tumors.

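### The SAP closes the best-response window at the 90-day visit, so some late or late-confirmed responses in patients who stop without progression may be missing from confirmed ORR

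*SAP*

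**What the plan says.** SAP 5.13.2 derives BOR from time point responses and names the periods that count: "All time point responses observed while on study treatment and during the short-term follow-up period will be included in the derivation". It separately drops responses after objective progression or after new anticancer therapy. It also says that CR and PR "should be confirmed by repeated assessment at least 4 weeks following the initial observation".

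Protocol Table JZDA.2.2, footnote a, fixes the end of the window. Short-term follow-up starts when patient and investigator agree that the patient "will discontinue study treatment and ends on the day of the 90-day follow-up visit".

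In the same table, the row "Tumor imaging/assessment" has a single mark, under the 30-day visit. Its instruction tells sites, for patients who stop without measured progression, to "continue to perform tumor assessment and imaging every 6 to 12 weeks according to the standard of care". Protocol 9.1 is softer: "Tumor assessments may continue for patients who are withdrawn from the study treatment for reasons other than disease progression every 6 to 12 weeks".

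Protocol 10.3.2 defines ORR by a best response of confirmed CR or PR and gives no follow-up cutoff. The SAP's rules for PFS (5.13.4, Table JZDA.5.2) and DoR (5.13.5) do not stop at the 90-day visit either.

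**The concern.** The response window and the imaging schedule do not fit together. Post-treatment scans can be up to 12 weeks apart, but only about 60 days of window remain after the 30-day scan. A later scan that PFS and DoR would use is not among those that SAP 5.13.2 lists for BOR.

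The patients concerned stop without progression and start no other therapy. For them, a response first seen after the 90-day visit falls outside BOR, and a response first seen at the 30-day scan may have its confirming scan fall outside. Such a patient is not a confirmed responder. TTR is then censored at the treatment start date (SAP 5.13.3), and the patient is left out of DoR, which covers confirmed responders only. Protocol 9.1.1.1 notes that "Response to immunotherapy may be delayed", so late responses are at least foreseeable.

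At stake is a possible understatement of confirmed ORR in cohorts of about 20, where one patient is visible in the estimate.

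**Working it through.** **The plan's own figure.** Protocol Table JZDA.10.1 gives exact (Clopper-Pearson) 95% limits at N = 20. Recomputed from beta quantiles:

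| Cases | Recomputed limits | Table |
|---|---|---|
| 0 | 0 to 0.168 | 0.0 to 0.17 |
| 3 | 0.032 to 0.379 | 0.03 to 0.38 |
| 5 | 0.087 to 0.491 | 0.09 to 0.49 |
| 10 | 0.272 to 0.728 | 0.27 to 0.73 |
| 15 | 0.509 to 0.913 | 0.51 to 0.91 |

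The table reproduces. The documents give no figure for the response window itself.

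**Inputs for the window**
- Post-treatment scan at nominal day 30, and window end at nominal day 90 (Protocol Table JZDA.2.2 and footnote a).
- Next scan after w weeks, w = 6 to 12, that is 42 to 84 days (Table JZDA.2.2; Protocol 9.1). I assume that the interval runs from the 30-day scan.
- Minimum gap for confirmation: 28 days (SAP 5.13.2).

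**Time left after the 30-day scan:** 90 − 30 = 60 days, and 60/7 = 8.57 weeks.

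**Day of the next scan = 30 + 7w**

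| Interval (weeks) | Day | In window? |
|---|---|---|
| 4 (optional confirmatory scan) | 58 | yes |
| 6 | 72 | yes |
| 7 | 79 | yes |
| 8 | 86 | yes |
| 9 | 93 | no |
| 10 | 100 | no |
| 11 | 107 | no |
| 12 | 114 | no |

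Every interval listed meets the 28-day minimum, so the window end is what decides.

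**Share of day-30 responses that the next scan cannot confirm in the window**
- All sites at 8 weeks or sooner: 0%. All at 9 weeks or later: 100%.
- Intervals spread evenly over 6 to 12 weeks (an assumption; the documents give no distribution): (84 − 60)/(84 − 42) = 24/42 = 57%.
- The same even spread, with each visit free to move by 7 days. Protocol Appendix 4 gives that tolerance for blood samples; none is stated for post-treatment scans.
  - Days 23 and 97: gap 74 days, (84 − 74)/42 = 24%.
  - Days 37 and 83: gap 46 days, (84 − 46)/42 = 90%.

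**Responses first seen after the 90-day visit.** These fall outside the listed periods whatever the scan interval.

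**Effect on ORR.** One patient in 20 is 1/20 = 5 points. As an illustration, 3/20 = 15% (95% CI 3.2% to 37.9%) becomes 2/20 = 10% (1.2% to 31.7%).

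**Effect on other measures.** A patient whose best response falls to SD still counts in DCR, so DCR is largely unaffected. SAP 5.13.6 requires no confirmation for irORR and states no 90-day limit of its own, so the confirmation gap does not reach that measure.

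**The case against.** The strongest reply is that the affected group is narrow and may be empty. A patient must stop without progression, start no new therapy and first respond at or after the 30-day scan. A response first seen on treatment can be confirmed at the 30-day scan if 4 weeks have passed. Sites that keep the study's 8-week rhythm would scan on day 86, inside the window. Protocol 9.1 also says that "tumor imaging for confirmation of response may be performed at the earliest 4 weeks after the first indication of response, or at the next scheduled" (meaning the next routine imaging visit). That sentence sits under the on-treatment heading, but nothing forbids such a scan afterwards. ORR is descriptive, with no hypothesis test. A bounded window is a legitimate choice when later scans are optional and irregular.

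Most of this stands, and it limits the point. It does not remove it: the SAP gives no reason for the bound, although Protocol 10.3 asks that changes from the protocol's methods be justified. The usual reasons for a bound, progression and new therapy, are already handled in the same SAP section.

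A reader might infer more than the documents support:
- That responses at the 30-day scan will often be lost. The 57% figure rests wholly on an assumed even spread of intervals.
- That TTR becomes undefined. SAP 5.13.3 censors it at treatment start.
- That the protocol and SAP must give different ORRs. The protocol is silent on a window, so values differ only if such a patient occurs.
- That many patients stop for toxicity, and that the protocol expects late responses in them particularly. No discontinuation rate is given, and the remark on delayed response concerns immunotherapy in general.

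**Conclusion.** The point holds in a limited form. Followed as written, SAP 5.13.2 leaves out a CR or PR first seen after the 90-day visit. It also prevents confirmation of one first seen at the 30-day scan when the next scan is more than 60 days later. The SAP does not expressly exclude later scans; the exclusion follows from its list of what is included.

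The number of patients affected cannot be derived from the documents. Among responses first seen at the 30-day scan, the share runs from 0% to 100% with site practice. The nominal day counts and the start of the interval at the 30-day scan are assumptions. The possible effect is an understatement of confirmed ORR by 5 points per lost responder in a cohort of 20, with the matching change in TTR and DoR. Sample size, error rates and the primary safety objective are untouched. This is a cheap improvement rather than a serious flaw.

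**What to change.** Replace the window sentence in SAP 5.13.2 with: *All time point responses from first dose until objective progression, start of new anticancer therapy or data cutoff, whichever is first, including those in long-term follow-up, will be included.*

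In SAP 5.13.6, state the corresponding window for the analyses based on RECIST 1.1 with a confirmatory scan, keeping the rule that responses after unconfirmed progression count. If the 90-day limit is intended, say so and give the reason.

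The cost is one replaced sentence and one added statement. The scans are those already foreseen for PFS and DoR, so the imaging schedule and patient management do not change. The new window removes the confirmation gap for a patient whose next scan takes place before data cutoff: days 72 to 114 would all count and all meet the 4-week minimum. The downside is that post-treatment scans follow standard of care and are less regular, so late responses are timed less precisely.
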